6.1.1. Primary Endpoint

The primary endpoint will be the log-transformed (\log_e) 28-day seizure rate for all PGTC seizures collected during the double-blind assessment phase (not including the 1-week double-blind taper phase). The 28-day seizure rate will be calculated as follows for the double-blind assessment phase:

$$\text{28-day seizure rate} = \frac{\# \text{ of seizures in the double-blind assessment phase of study}}{\lceil \# \text{ of days in period} - \# \text{ of missing diary days in period} \rceil} \times 28$$

When the log-transformation is used, the quantity “1” is added to the 28-day seizure rate for all subjects to account for any possible “0” seizure incidence. This will result in the following primary efficacy endpoint: $\log_e(28\text{-day seizure rate} + 1)$.

The 28-day seizure rate for all PGTC seizures collected during the baseline phase will be calculated similarly.

6.1.2. Secondary Efficacy Endpoint

Responder Rate, defined as subjects who have a $\geq 50\%$ reduction in the 28-day seizure rate for all PGTC seizures during the double-blind assessment phase, as measured from baseline (data collected during the 8-week baseline phase) will be defined as a responder, otherwise they be considered as a non-responder.

The responder rate will be based on the percentage change from baseline in the 12-week double-blind treatment phase 28-day seizure rate, which is defined as follows:

$\% \text{ Change} = [(28\text{-day seizure rate}_t - 28\text{-day seizure rate}_b) / 28\text{-day seizure rate}_b] \times 100\%$, where t is the 12-week double-blind treatment phase and b is for the 8-week baseline phase.

6.1.3. Exploratory Endpoints

6.1.3.1. Proportion of Seizure-Free Days

The proportion of seizure-free days for each seizure type: PGTC, myoclonic, tonic/tonic, absence, and clonic seizures will be computed. Proportion of PGTC seizure-free days is defined as number of seizure-free days in a period divided by “number of days in a period - number of missing Seizure diary days”.

6.1.3.2. Number of Seizure-Free Days Gained

The number of seizure-free days gained for each seizure type: PGTC, myoclonic, tonic/tonic, absence, and clonic seizures will be calculated. The number of seizure-free days will be adjusted to a per 12 weeks value (ie, 84 days) for the baseline and 12-week double-blind assessment phases. Changes from baseline are to be computed and the analysis performed accordingly. The 12 week adjusted number of seizure-free days is defined as follows:

number of seizure-free days in a period * 84 / (number of days in a period – number of missing diary days in a period) .

Period refers to the length time in baseline, and in DB. The 12 week adjusted number of seizure-free days will be calculated for baseline and DB; change from baseline will also be calculated.

6.1.3.3. Proportion of Subjects with PGTC Seizure-Freedom

The proportion of subjects with PGTC seizure-freedom will be computed. The numerator for seizure-freedom is defined as the number of subjects that experience no PGTC seizures over the last 28 days of the double-blind assessment phase (must be a minimum of 4 weeks), patient must have received at least 42 days (2 weeks + 28 days) of study medication and have a minimum of 21 of the last 28 days as non-missing diary (ignore the first 2 weeks from dose escalation phase). The denominator is the number of subjects in the ITT population with 42 days (2 weeks + 28 days) of study medication.

The proportion of subjects with PGTC seizure-freedom over the entire double blind fixed dose assessment phase will also be computed. The numerator for seizure-freedom is defined as the number of subjects that experience no PGTC seizures over the fixed dose phase, patient must have received at least 84 days (2 weeks + 14 +28 +28 days) dosing and have a minimum of 11 of the 14 days and 21 of each of the two 28 day periods with non-missing seizure diary (ignore the first 2 weeks from dose escalation phase). The denominator is the number of subjects in the ITT population with 84 days of study medication.

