2.3. Study Objectives

Primary Objective:

- To demonstrate superior efficacy of pregabalin compared to placebo for treatment of PGTC seizures as measured by the 28 day seizure rate.*

Safety Objectives:

- To assess the safety and tolerability of pregabalin relative to placebo in pediatric and adult subjects with PGTC seizures.*

Secondary Objectives:

- To demonstrate superior efficacy of pregabalin compared to placebo for PGTC seizures as determined by responder rate.*

Exploratory Efficacy Objectives:

- To demonstrate superior efficacy of pregabalin compared to placebo as determined by seizure-free days for PGTC, myoclonic, tonic/tonic, absence, and clonic seizures.*

- *To demonstrate superior efficacy of pregabalin compared to placebo as determined by seizure-freedom of PGTC seizures over the last 28 days of the double-blind assessment phase and over the entire double-blind assessment phase. In those subjects with myoclonic, tonic/tonic, absence, or clonic seizures at baseline, seizure freedom over the last 28 days of the study and over the entire double-blind assessment phase will be summarized descriptively.*
- *To demonstrate superior efficacy of pregabalin compared to placebo as determined by the time to experience the same total number of PGTC seizures in the 12-week double-blind assessment phase that was observed during the baseline phase for each subject (referred to as 'Time to Nth Seizure'). This analysis will be reported separately from the main clinical study report.*

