5. ANALYSIS SETS

5.1. Full Analysis Set (Intent-to-Treat Population)

The efficacy analyses will be performed on the intent to treat (ITT) population which consists of randomized subjects who took at least 1 dose of investigational product during the double-blind assessment phase, have a baseline value and at least 1 post-baseline efficacy assessment (diary entry).

5.2. 'Per Protocol' Analysis Set (PP Population)

None. Protocol Deviations will be addressed (See [Section 5.6](#)) but no PP analyses are planned.

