8. STATISTICAL METHODOLOGY AND STATISTICAL ANALYSES

The ITT population will be used in the analyses of the primary efficacy endpoint, and for all other efficacy endpoints. The Safety population will be used in the analyses of the safety data.

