8.5. Summary of Efficacy Analyses

Endpoint (Key Summary Metrics)	Analysis Set	Statistical Method	Model/ Covariates/ Strata	Missing Data	Interpretation
Log _e 28-day PGTC seizure rate (N, LS Mean Diff/SE)	ITT	ANCOVA	Treatment, region, age strata, baseline seizure rate	Days missing from Seizure Diary will be subtracted from rate calculations	Primary Analysis Note: age strata is protocol defined age strata. Baseline is the log of 28-day PGTC rate at baseline
Key summary statistics will be presented for the Log _e 28-day PGTC seizure rate and for the back transformed “percent reduction in seizures” relative to placebo.					
Log _e 28-day PGTC seizure rate (N, LS Mean Diff/SE) (treatment-by-age p-value)	ITT	ANCOVA	Treatment, region, age group, treatment-by-age group interaction, baseline seizure rate	Days missing from Seizure Diary will be subtracted from rate calculations	Supplemental Analysis Note: age groups are Age < 17 yrs and Age ≥ 17 yrs. Baseline is the log of 28-day PGTC rate at baseline.
Key summary statistics will be presented for the Log _e 28-day PGTC seizure rate and for the back transformed “percent reduction in seizures” relative to placebo.					
Responder rate (%)	ITT	Logistic regression	Treatment, region, age strata	Days missing from Seizure Diary will be subtracted from rate calculations	Secondary Analysis
Proportion Seizure-free days (%)	ITT	ANCOVA	Treatment, region, age strata, baseline	Days missing from Seizure Diary will be subtracted from rate calculations	Exploratory Analysis Each seizure type: PGTC, myoclonic, tonic/tonic, absence, and clonic seizures. Baseline for this endpoint is the proportion of seizure free days at baseline.
Number of seizure-free days gained (N, Mean, SE)	ITT	ANCOVA	Treatment, region, age strata, baseline	Days missing from Seizure Diary will be subtracted from rate calculations	Exploratory Analysis Each seizure type: PGTC, myoclonic, tonic/tonic, absence, and clonic seizures. Baseline for this endpoint is the number of adjusted seizure free days at baseline.

Proportion PGTC Seizure-freedom (%)	ITT	Logistic regression	Treatment, region, age strata	Days missing from Seizure Diary will be subtracted from rate calculations	Exploratory Analysis
Log _e 28-day PGTC seizure rate (N, LS Mean Diff/SE)	ITT	ANCOVA	Treatment, region, age strata, baseline	Multiple imputation will be applied.	Sensitivity Analysis. Baseline is the log of 28-day PGTC rate at baseline.

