Number of seizure-free days gained	The number of seizure-free days will be adjusted to a per 12 weeks value (ie, 84 days) for the baseline and 12-week double-blind assessment phases. Changes from baseline are to be computed and the analysis performed accordingly. Number of 12 week adjusted seizure free days is defined as follows: Number of seizure free days in a period x 84 / number of days in a period.
Proportion PGTC Seizure-freedom	The numerator for seizure-freedom is defined as the number of subjects that experience no PGTC seizures over the last 28 days of the double-blind assessment phase (Patient must have received at least 42 days (2 weeks + 28 days) of study medication and have a minimum of 21 of the last 28 days as non-missing diary). The denominator is the ITT population with 42 days (2 weeks + 28 days) of study medication.

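### Exploratory PGTC seizure-freedom is labelled ITT, but its denominator keeps only ITT subjects with 42 or 84 days of medication, so the treatment comparison is not protected by randomisation

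*SAP*

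**What the plan says.** **Population.** SAP Section 8: "The ITT population will be used in the analyses of the primary efficacy endpoint, and for all other efficacy endpoints". The row "Proportion PGTC Seizure-freedom" in the Section 8.5 table also gives ITT as the analysis set, with logistic regression on treatment, region and age strata. Under Section 5.1, ITT needs randomisation, one dose in the double-blind assessment phase, a baseline value and one post-baseline diary entry. No minimum exposure is set.

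**Denominators.** Section 6.1.3.3 defines two proportions.
- Last 28 days: "The denominator is the number of subjects in the ITT population with 42 days (2 weeks + 28 days) of study medication". Appendix 1 repeats this: "The denominator is the ITT population with 42 days (2 weeks + 28 days) of study medication".
- Fixed dose phase: "The denominator is the number of subjects in the ITT population with 84 days of study medication".

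Both numerators also set minimum numbers of non-missing diary days, and both carry the instruction "ignore the first 2 weeks from dose escalation phase".

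**Objective and test.** Section 2.3 lists superiority to placebo on seizure-freedom as an exploratory objective, over the last 28 days and "over the entire double-blind assessment phase". Section 8.3 plans logistic regression with nominal two-sided p-values and no multiplicity adjustment.

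**Rationale.** The amendment log (Amendment 2, item 13) says the definition was clarified to agree with the adult PGTC definition used in past pregabalin studies.

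**The concern.** How long a subject stays on medication can depend on the assigned treatment. The SAP expects this: Section 7 sets up drop-out patterns for lack of efficacy and for adverse events, and Section 3.1 lists four seizure-related reasons for discontinuation. A subject who leaves for one of these reasons before the threshold is not counted as a failure but is removed. If removal differs between arms, the two proportions can differ with no treatment effect on the share of all ITT subjects who become seizure-free.

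Someone reading only Section 8.5 would take the result as an ITT comparison, and no all-ITT version of this endpoint is planned to show the difference. At stake is the reading of an exploratory superiority objective.

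Separately, the objective covers the whole double-blind assessment phase, but the endpoint leaves out the two escalation weeks.

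**Working it through.** **1. Thresholds.** Section 6.1.3.3 builds them as 14 + 28 = 42 days and 14 + 14 + 28 + 28 = 84 days. Section 2.1 gives the double-blind assessment phase as 12 weeks, and 12 × 7 = 84 days. The first threshold is therefore 42/84 = 50% of the phase and the second is 100% of it.

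**2. Who is lost and who is kept.**

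| Subject | 42-day version | 84-day version |
|---|---|---|
| Stops before day 42 | removed | removed |
| Stops between day 42 and day 84 | kept | removed (unless taper doses count) |
| Enough medication, too few diary days | kept, cannot be in the numerator | kept, cannot be in the numerator |

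Missing diary days thus count as failure, while stopping medication early leads to removal. The responder endpoint does neither for early stoppers with no rate: Appendix 1 sets a subject with a baseline rate but no double-blind rate to non-response.

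**3. Size for the 84-day version.** The plan gives no expected rate, drop-out figure or power for seizure-freedom, so there is no stated figure to reproduce. Let p be the share of all ITT subjects who are seizure-free, with those short of the threshold counted as not free, and let d be the share short of the threshold. The SAP proportion is then p / (1 − d). Assume p = 15% in both arms, so no difference on the all-ITT measure.

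| d placebo | d pregabalin | SAP rate, placebo | SAP rate, pregabalin | Odds ratio |
|---|---|---|---|---|
| 5% | 20% | 0.15/0.95 = 15.8% | 0.15/0.80 = 18.8% | 1.23 |
| 10% | 25% | 0.15/0.90 = 16.7% | 0.15/0.75 = 20.0% | 1.25 |
| 10% | 10% | 16.7% | 16.7% | 1.00 |
| 20% | 5% | 18.8% | 15.8% | 0.81 |

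**4. Against sampling error.** With the 56 per group of Section 2.1, the first row leaves 56 × 0.95 = 53.2 and 56 × 0.80 = 44.8 subjects. The pooled proportion is 16.8/98 = 0.171. The standard error is √[0.171 × 0.829 × (1/53.2 + 1/44.8)] = 7.6 percentage points, against a shift of 3.0 points. Simulating this scenario with a pooled z-test gives a two-sided rejection rate of about 7%, against about 5% when all ITT subjects are in the denominator.

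**5. Range.** For assumed p of 10% to 30% and unequal loss from 5% against 15% up to 5% against 30% (more on pregabalin), the spurious odds ratio runs from 1.13 to 1.63 and the rejection rate from 5.3% to 20.2%. The upper end needs both the widest imbalance and p = 30%.

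**6. Period.** Section 2.1 includes the 2-week escalation in the double-blind assessment phase. Under Section 6.1.3.3 a subject with PGTC seizures only in those two weeks can be counted as free, although the objective in Section 2.3 covers them. This needs no assumption.

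**The case against.** The restriction is deliberate and openly stated. Section 6.1.3.3 and Appendix 1 describe a subset of ITT, and the amendment log gives comparability with past studies as the reason. That stands, and it justifies keeping the present definition in the report. It does not justify an unqualified ITT label or the lack of an all-ITT analysis.

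The endpoint is exploratory with nominal p-values, and Section 4.2 confines claims to the primary endpoint. That also stands and limits the weight of the point.

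Three stronger readings are tempting but not supported:
- *That drop-outs disappear from seizure-freedom altogether.* This is essentially true of the 84-day version only. The 42-day version keeps subjects who stop after reaching 42 days.
- *That the definition favours pregabalin.* The documents give no discontinuation rates. Withdrawal for lack of efficacy or worsening seizures may be commoner on placebo, which would reverse the shift. With equal losses both rates are inflated but the comparison does not move in this model.
- *That a completer whose last dose falls on day 82 or 83 is excluded.* Section 2.1 has study drug continuing into a 1-week taper, and the SAP does not say whether those days count towards 84. If they do, such a subject can still qualify.

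**Conclusion.** The label and the denominator conflict, and both denominators condition on a post-randomisation outcome. The logistic comparison is therefore not protected by randomisation. The effect is greatest for the 84-day version, which is in effect a completer analysis, and more limited for the 42-day version.

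The size cannot be fixed from the documents. Under the assumed 15% seizure-free in both arms and 5% against 20% falling short of 84 days, a 3-point difference (15.8% against 18.8%) arises from the denominator alone, less than half its standard error at 56 per group. The direction depends on which arm loses more subjects. These figures treat everyone short of the threshold as not seizure-free.

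The mismatch between the period in Section 2.3 and that in Section 6.1.3.3 holds on the text alone. The primary analysis, its type I error and the secondary responder analysis are untouched. The change is worth making because it is cheap and removes a selection effect from a comparison that will be reported with p-values.

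**What to change.** 1. Analyse both versions of seizure-freedom on all ITT subjects, counting those short of the exposure or diary threshold as not seizure-free.
2. Keep the present definition as a supportive, exposure-qualified table for comparison with past pregabalin studies, and label it so in Section 8.5, with a matching qualification in Section 8.
3. In Section 6.1.3.3, state whether taper-week dosing counts towards the 84 days, or replace the day count with completion of the double-blind phase.
4. Reconcile Section 2.3 with Section 6.1.3.3, either by adding a version covering the whole assessment phase or by naming the fixed dose phase in the objective.

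The cost is SAP wording and one additional table, with no new data. Reported proportions will be lower than under the present definition wherever subjects fall short of the exposure threshold.

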6.1.3.4. Time to Nth Seizure

The time to experience the same total number of PGTC seizures in the double-blind phase that were observed during the baseline phase for each subject, referred to as ‘Time to Nth

'Seizure' will be assessed as an exploratory endpoint and will be described and conducted according to a separate exploratory statistical analysis plan (ESAP) for endpoint development, and reported separate from the main clinical study report.

6.2. Safety Endpoints

Safety endpoints include adverse event data (eg, occurrence, nature, intensity, and relationship to study drug), Hy's law, vital signs, weight, clinical laboratory assessments, ECG, neurological examination, physical examination, prior and concomitant medications, suicidal ideation and behavior assessments (as age appropriate).

6.2.1. Adverse Events

All AEs occurring during the course of the study will be coded using the MedDRA coding dictionary.

All AEs (serious and non-serious) reported from the first day of study treatment through and including 999 calendar days after the last administration of the study drug will be considered treatment emergent AEs (TEAEs).

6.2.2. Prior and Concomitant Treatments and Medications

Concomitant and prior medications, defined as medications stopped, ongoing or started on or after the first day of study treatment up to the last dose of study treatment, will be summarized, using the WHO-drug coding dictionary. In addition, concomitant and prior non-drug treatments/procedures will be summarized using the MedDRA coding dictionary.

6.2.3. Suicidal Ideation and Behavior Assessments During the Clinical Trial

C-SSRS responses will be mapped to the Columbia Classification Algorithm of Suicide Assessment (C-CASA). (see [Appendix 2](#))

The following 3 endpoints are for suicidality data analysis and evaluation:

- Suicidal Behavior;
- Suicidal Ideation;
- Suicidal Behavior or Ideation.

Suicidal behavior: A subject is said to have suicidal behavior if the subject has experienced any of the following events (C-CASA event codes 1-3):

- Completed suicide;
- Suicide attempt; or
- Preparatory acts toward imminent suicidal behavior.

Suicidal ideation: Any observed suicidal ideation maps to a single C-CASA category. The C-SSRS, for example, includes five ideation questions (that map to C-CASA category 4) with increasing severity.

Subjects with new onset suicidal ideation and behavior: A subject will be considered to have a new onset of suicidal ideation and behavior if the subject reported no ideation and no behavior at the baseline assessment (note that self-injurious behavior, no suicidal intent [C-CASA code 7] is not considered to be suicidal ideation or behavior) and reported any behavior or ideation post-baseline. Data observed at screening is not considered in the definition of new onset.

Subjects with worsening suicidal ideation and behavior relative to baseline: A subject will be considered to have a worsening of suicidal ideation and behavior if the subject moved to a lower numbered C-CASA category (observed in categories 1-4) than was reported at baseline. Movement within C-CASA categories 5-9 would not be considered worsening. In addition, worsening will be considered within the suicide ideation C-CASA category 4 if there is an increase in severity identified in the C-SSRS which captures additional granularity on suicide ideation. A subject who reports only ideation at baseline and who reports any behavior post-baseline is considered to have worsened. Data observed at screening is not considered in the definition of worsening.

6.3. Other Endpoints

6.3.1. PK/PD Endpoints

PK/PD endpoints and analyses will be described in a separate document created by Clinical Pharmacology.

6.4. Covariates

Log-transformed 28-day seizure rate [$\log_e(28\text{-days seizure rate}_b + 1)$] at baseline will be utilized as a covariate in the linear model used in the primary analysis, and for secondary analyses utilizing a similar model.

Additional terms considered in the primary analysis and included in the responder rate analysis are age strata and geographic region. Because it is anticipated that this study will have many investigator centers having very few subjects in each treatment group, age strata, and geographic region combination; a pre-specified pooling will take place (See [below](#)).

Two covariates about age are defined as follows.

Age strata will be defined as Stratum 1: 5-7 years of age; Stratum 2: 8-11 years of age; Stratum 3: 12-16 years of age; or Stratum 4: 17-65 years of age. This covariate is applied to primary analysis.

Age group will be defined as: group 1, 5-16 years of age (at randomization); group 2: 17-65 years of age (at randomization). This covariate is applied to the analysis of primary efficacy endpoint as a sensitivity analysis. This age group definition will also be used to investigate treatment-by-age interaction for the primary efficacy endpoint.

Age will be defined as subjects' age at randomization. If a subject turns 66 at randomization after screening, he/she will be counted in the 17-65 age group.

Region will be defined as follows (Upon closing of the randomization, region determinations will be further evaluated-See [contingency plan](#)):

- *United States (US)*: Subjects who participate in the U.S. or Puerto Rico centers will be pooled together;
- *European Union*: All subjects who participate in European Union (eg, Austria, Belgium, Denmark, France, Germany, Greece, Italy, Netherlands, Portugal, Spain, Sweden, United Kingdom, Bulgaria, Croatia, Czech Republic, Estonia, Hungary, Lithuania, Poland, Romania, and Slovakia,) centers will be pooled together. The member countries of European Union are explained in more detail at https://europa.eu/european-union/about-eu/countries_en;
- *Asia-Pacific*: All subjects participating in Asia-Pacific (China, India, Korea, Malaysia, Philippines, Singapore) centers will be pooled together;
- *Others*: All subjects not participating in above three regions (eg, Russian Federation, Ukraine, Belarus, Bosnia and Herzegovina, Serbia, Montenegro, Turkey) centers will be pooled together.

Any region not enrolling any subjects will not be included in the analysis.

